2.4.2 Selection of biomarkers for pilot trial

Given the likelihood that lignans serve as partial estrogen antagonists in a high estrogen environment [52,53,55,83], risk biomarkers were selected that were likely to be modulated by selective estrogen receptor modulators (SERMs), as well as those likely to be modulated by lignans for the pilot trial in premenopausal women [84]. The initial risk biomarker set included cytromorphology and Ki-67 in hyperplastic breast epithelium in tissue sampled by RPFNA,

mammographic breast density, serum bioavailable estradiol, testosterone, and IGF-I:IGFBP-3 [85-90]. Subsequently serum adiponectin, leptin and cytokine assays [57,61-66,91,92] were added given the emergence of data that several of these markers - particularly adiponectin and possibly leptin - may be risk factors for breast cancer. Adiponectin counteracts the promotional effects of leptin on the PI3 kinase and mTOR pathways [93], reduces insulin and insulin resistance [94], and blocks cell entry into S phase [95], whereas cytokines promote tissue aromatase activity, increasing estradiol. Change in Ki-67 in areas of cytologic hyperplasia was chosen as the primary endpoint using the following rationale. It had previously been established in a prospective study that cytologic atypia in tissue sampled by random periareolar fine needle aspiration (RPFNA) was a strong risk biomarker for breast cancer [85]. When utilized in women at increased risk for cancer between the ages of 30 and 60, it was associated with a 5-fold increase in the risk of DCIS and invasive cancer and could stratify short term risk based on the Gail model despite being used in women already at increased risk for the disease [96]. However, hyperplasia with atypia is not a practical primary response endpoint for Phase II prevention studies because based on prior studies [97] it would require screening aspiration of 4-5 pre-menopausal women to enroll one woman with atypia. Further requiring baseline atypia would limit generalizability of results. Consequently, the proliferation biomarker Ki-67 assessed in areas of hyperplasia was chosen as the primary endpoint. Ki-67 is currently acceptable as a primary endpoint in Phase II prevention trials for the following reasons [80]:

- Proliferation plays a fundamental role in carcinogenesis.
- Ki-67 expression is positively associated with pre-cancerous changes of histologic and cytologic atypia [86].

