2.4.3 Eligibility criteria for SDG pilot study

Eligibility criteria included regular menstrual cycles, no oral contraceptives, a 3-fold or greater increase in 5-year estimated risk for breast cancer relative to SEER statistics for age group, and normal mammogram performed in the follicular phase of the menstrual cycle within 3 months of baseline RPFNA. Subjects on oral contraceptives were excluded in order to reduce subject hormonal heterogeneity and because it might be more difficult to demonstrate biomarker modulation from SDG in the face of exogenous hormones. Baseline RPFNA was also to be performed in the follicular phase and had to show unequivocal hyperplasia +/- atypia as well as a minimum Ki-67 expression of 2% in hyperplastic ducts. The Ki-67 value of 2% was chosen since this is the median Ki-67 value in hyperplastic tissue obtained by RPFNA from high risk pre-menopausal women in the follicular phase of the cycle [86]. Further, a Mayo Clinic series suggests that women having a biopsy showing atypical hyperplasia and a Ki-67 of 2% or higher have a significantly higher 10-year risk of breast cancer (14% versus 3%) [88]. The early-mid follicular phase is utilized due to greater subject comfort and less bleeding during RPFNA.

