3.0 SUMMARY OF STUDY PLAN

The favorable outcome of the pilot study suggests progression to a Phase II multi-institutional placebo-controlled trial of 12 months of Brevail® (50 mg SDG) in moderate and high risk premenopausal women. Modulation of Ki-67 in women with baseline Ki-67 of 2% or greater in hyperplastic tissue is the primary endpoint rather than normalization of atypia, so as to limit the number of women who would need to be screened by RPFNA to 2-3 for every woman going on trial (vs. 4-5 if all had to have atypia). Other risk biomarkers will be measured, as well as impact on quality of life, change in breast pain in those with mastalgia at baseline, and surrogate markers of fertility. These considerations will be important for eventual uptake of SDG as a prevention agent. Mechanisms of action will also be explored. Similar eligibility criteria are used as in the pilot study, where the average percentage of cells expressing Ki-67 at baseline was 6.4% (median 4%) with an average change of -3.7% with a common standard deviation of 5.5%.

The study eligibility is being altered approximately 2.5 years after study start to allow inclusion of women on oral contraceptives. This will both widen application of results should they be positive and is expected to at least double the rate of accrual. Assessment of difference in change in Ki-67 between women randomized to SDG versus placebo can be accomplished with a 2:1 randomization of 242 women. Assuming a dropout rate of 10%, with 220 evaluable subjects there will be 83% power to detect a 2.5% reduction in Ki-67 for the treatment group compared to no reduction in the control group; this will be our primary endpoint. This is based on an assumption of a common standard deviation of 6% for change in Ki-67 in both the no oral contraceptive and oral contraceptive groups and a Type I error rate of 5%

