11.2 Statistical Analysis

All analyses will be intent-to-treat. All subjects randomized will be evaluable for safety and all subjects that have both a pre and post specimen are evaluable for efficacy. Primary analysis of efficacy will be performed on all evaluable subjects and secondary analysis will be done on those subjects who received at least 6 months of study medication and were confirmed as being in the follicular phase for both RPFNA procedures. From our experience we have very little missing data; however, if the missing data rate is above 5%, we will use multiple imputation to impute these values to perform the primary and secondary analyses.

The primary outcome will be change in Ki-67 (percent of cells expressing Ki-67) from baseline to 12 months. The two-sample t-test will be used to compare the change in Ki-67 between the SDG

and placebo groups. Any difference in baseline values of Ki-67 between the two groups would be due to chance, however, if there is a significant difference, then analysis of covariance adjusting for baseline values will be performed. Due to potential skewness in these variables we will assess whether or not the Central Limit Theorem may be assumed. Given the sample size the existence of an extremely high degree of skewness would require the use of the Wilcoxon Signed Rank test.

For the secondary endpoints, similar methods as above will be used to compare the treatment and control groups at two time points for all markers, i.e., serum hormones and clinical laboratory tests. We will also correlate change in the primary biomarker Ki-67 with change in other markers (e.g., bioavailable estradiol, cytokines, RTqPCR results) using Pearson's correlation coefficient. Again, if there exists a high degree of skewness in these variables, Spearman's correlation will be utilized.

Multiple regression analysis will also be used to investigate whether changes in Ki-67 are due to variables other than treatment effect (e.g., age, cytromorphology, Gail risk; as well as the predictive effect of other biomarkers on modulation of Ki-67). Best subsets and stepwise approaches will be employed while controlling for treatment group.

For comparison of moderate or worse toxicities we will consider grade 3 toxicity or premature trial discontinuation as the critical events. The prevalence of events in the SDG vs. the placebo arm will be examined by Fisher's exact test.

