5.1 Breast Tissue Cytomorphology

Two slides are made from each pooled sample by a liquid-based technique (ThinPrep®): two for cytomorphology under RNAse-free conditions one of which will undergo microdissection, processing to RNA and then cDNA and frozen at -80°C until later use for RT-qPCR. Remaining cells will be left in PreservCyt® for later use for RT-qPCR. Initial cytomorphologic assessment is performed by the cytotech and then the slide is photographed and sent to the cytopathologist, [name] for final assessment. Slides will be given both a categorical classifier (non-proliferative or normal, hyperplasia, hyperplasia borderline atypia, atypical hyperplasia, or suspicious for cancer) and a Masood Index score [106]. The Masood score is the result of 1-4 points given for 6 different morphologic characteristics: cellular arrangement (monolayer, overlapping nuclei, clustering, loss of cohesion), pleomorphism, myoepithelial cells (many, moderate, few, absent); anisonucleosis (absent, mild, moderate, conspicuous); nucleoli (absent, micronucleoli, micro and rare macronucleoli, predominately macronuclei); and chromatin clumping (absent, rare, occasional, frequent). Change in Masood score will be assessed by subtracting the off-study score from the baseline score

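### The regression of Ki-67 change does not name or force in baseline Ki-67, so baseline cytomorphology can appear to explain change through regression to the mean

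*Combined protocol and SAP*

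**What the plan says.** Section 11.2 defines the outcome: "The primary outcome will be change in Ki-67 (percent of cells expressing Ki-67) from baseline to 12 months". After the comparison of arms it plans a multiple regression to "investigate whether changes in Ki-67 are due to variables other than treatment effect (e.g., age, cytromorphology, Gail risk" and the predictive effect of other biomarkers). On model building it says: "Best subsets and stepwise approaches will be employed while controlling for treatment group". Baseline Ki-67 appears once as an adjustment, in the comparison of arms, and only conditionally: "if there is a significant difference, then analysis of covariance adjusting for baseline values will be performed". That sentence does not reach the regression. Section 11.2 does not say whether cytomorphology means the baseline reading or its change.

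Three other places bear on this.

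- **Link between the markers.** Section 2.4.2 states that "Ki-67 expression is positively associated with pre-cancerous changes of histologic and cytologic atypia", without giving a strength.
- **Selection at entry.** Section 3.0 says that modulation of Ki-67 in "women with baseline Ki-67 of 2% or greater in hyperplastic tissue is the primary endpoint", and section 4.4.3 makes 2% an entry criterion. Section 2.4.3 explains that 2% was chosen for the pilot "since this is the median Ki-67 value in hyperplastic tissue obtained by RPFNA from high risk pre-menopausal women in the follicular phase" of the cycle.
- **Shared specimen.** Appendix 1, section 5.1 says of cytology: "Two slides are made from each pooled sample by a liquid-based technique". Section 5.3 takes the Ki-67 slide from the preserved material of the same aspirate and scores the ducts with the densest staining.

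**The concern.** Change is 12-month Ki-67 minus baseline Ki-67, so baseline enters the outcome with a minus sign. Women are admitted because their baseline reading was at or above the population median. Some of those readings were high by chance of sampling and will fall back at 12 months in both arms. If an aspirate that happens to catch more proliferative ducts also tends to be read as atypical, women with atypia will fall further for that reason alone. A model without baseline Ki-67 would credit the difference to atypia.

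At stake is the interpretation of one secondary analysis. Its aim is worded causally, and section 11.2 tests secondary, tertiary and exploratory analyses at a two-sided 5% level without multiplicity control. A false driver of Ki-67 change would therefore meet no later check.

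**Working it through.** **Inputs from the documents.** 220 evaluable women, 2:1 allocation, SD of change 6 points, difference 2.5 points, two-sided 5% (section 11); entry at Ki-67 of 2% or more; pilot baseline median Ki-67 4% and atypia 62% (section 2.4.4.2).

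**Assumed, because the documents do not give them.** The baseline SD, the test-retest correlation rho of Ki-67, and the correlation r between cytology and baseline Ki-67. The pilot averages cannot settle these: section 3.0 gives a mean baseline of 6.4% and mean change of -3.7, and section 11.1 gives 4% and -2.4.

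**1. The plan's own figure.** SE = 6 × sqrt(1/146.67 + 1/73.33) = 0.858; 2.5/0.858 = 2.91; power = Φ(2.91 - 1.96) = 0.83. The stated 83% reproduces. The plan gives no figure for the regression.

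**2. Where the artefact comes from.** Write baseline as T + e0 and 12-month as T + e1, where T is the woman's stable level and e0, e1 are visit-specific variation. Without treatment, change = e1 - e0. For a baseline predictor C unrelated to e1, before any entry cut, cov(change, C) = -cov(e0, C). The stable part cancels. The artefact therefore needs C to share e0; correlation with baseline Ki-67 is not enough.

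**3. Plausible rho.** With equal variances, SD of change = s × sqrt(2(1 - rho)), so rho = 1 - 36/(2s²) for an SD of 6. An assumed s of 5, 5.5, 6 or 7 gives rho = 0.28, 0.41, 0.50 or 0.63.

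**4. Analytic size.** If C relates to follow-up only through observed baseline Ki-67, corr(change, C) = -r × sqrt((1 - rho)/2). For r = 0.2 and rho = 0.5 this is -0.10. Then λ = 0.10 × sqrt(220)/sqrt(1 - 0.01) = 1.49, and the chance of nominal significance is Φ(1.49 - 1.96) + Φ(-1.49 - 1.96) = 0.32. Over r = 0.1-0.4 and rho = 0.3-0.7, the correlation runs from -0.04 to -0.24 and the false-positive chance from 9% to 95%.

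**5. Simulation with the entry cut.** 220 women, no treatment effect, log-normal Ki-67 with screening median 2%, entry at 2% or more, atypia 62%, rho 0.4-0.6, r 0.2-0.4 before the cut, 800 runs per setting. Enrolled baseline median was about 3.9% and SD of change 5.7-6.5, close to the pilot median and the planned SD. Mean Ki-67 fell by about 0.8-1.2 points with no treatment at all. Results for atypia (coefficient in points; false-positive rate):

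| Atypia linked to | Baseline Ki-67 omitted | Baseline Ki-67 included |
|---|---|---|
| Observed baseline Ki-67 | -0.5 to -1.3; 8-31% | -0.01 to +0.12; 3-5% |
| Visit-specific part only | -1.2 to -2.8; 26-94% | -0.5 to -1.9; 12-79% |
| Stable level only | +0.1 to +0.4; 4-5% | +0.6 to +1.7; 15-74% |

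The first row sits low in the analytic range because the entry cut reduces the correlation between atypia and baseline Ki-67 to about 0.11-0.23.

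**6. Intermediate cases.** With atypia linked to observed baseline, or equally to the stable and visit-specific parts, and rho 0.4-0.6, false positives were 11-42% without baseline and 4-5% with it. With rho 0.3-0.7 and atypia tracking observed baseline or sharing visit-specific variation, they were 16-51% without and 4-30% with. When the stable part dominated (0.3 against 0.15), adjustment gained little: 6-14% before, 6-11% after.

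**7. Precision.** With equal variances, baseline explains (1 - rho)/2 of the variance of change. Including it multiplies the standard error of an unrelated predictor by sqrt(1 - (1 - rho)/2): 0.81 at rho = 0.3 and 0.92 at rho = 0.7, a reduction of 8-19%.

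**The case against.** There is a good case on the other side, and much of it stands.

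- **The covariate list is open.** It is introduced as a set of examples, so a reader who infers that baseline Ki-67 is excluded goes beyond the text. What stands is that it is not named and not guaranteed: stepwise selection may drop any term that is not forced in.
- **Correlation with baseline Ki-67 is not sufficient.** A reader might infer that every correlate of baseline Ki-67 must correlate with change, so that atypia is bound to look like a driver. Step 2 shows otherwise. Section 2.4.2 reports an association but not whether it lies in the stable or the visit-specific part. The shared aspirate makes a purely stable link less plausible but cannot exclude it.
- **Adjustment is not a full cure.** For a predictor that is not randomised, neither the change-score model nor the baseline-adjusted model is right by default. If cytology tracks only the stable level, adjusting for a noisy baseline creates a positive artefact where there was none. This stands, and it is why one adjusted model should not be the only report.
- **Cytomorphology may mean its change.** Appendix 1, section 5.1 defines a change in Masood score, so the text allows that reading. It needs clarifying either way.
- **The analysis is not primary, and section 11.2 accepts more false positives outside the primary endpoint.** That limits the weight of the point. But the acceptance concerns multiple testing; it does not address bias in a single test.

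**Conclusion.** The point holds as a modest one. The regression does not secure baseline Ki-67 as a covariate, in a trial that selects on baseline Ki-67 and reads both markers from one aspirate. A spurious negative association between atypia and Ki-67 change is a real risk but not a certainty. Under moderate assumptions it would reach nominal significance in roughly 10-50% of trials. The rate is higher if cytology shares only visit-specific variation, and stays at the nominal 5% if it shares only the stable level. These figures rest on assumed correlations and on cytomorphology being the baseline value.

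A reader might also infer that the SDG effect is biased. The documents do not support that: treatment is randomised, so baseline cytology does not differ systematically by arm, and the comparison of arms is a separate analysis. Severity: consider.

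**What to change.** In the multiple-regression paragraph of section 11.2:

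1. State that cytomorphology is the baseline value.
2. Force baseline Ki-67 and treatment group into every model of Ki-67 change, or equivalently model 12-month Ki-67 with baseline as a covariate.
3. Report each predictor with and without baseline Ki-67. A result that appears in only one version should be read as uncertain.
4. Describe findings as associated with Ki-67 change rather than as causes of it.

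The cost is a few sentences and one covariate already measured in every evaluable woman. Some predictors will look weaker after adjustment. Adjustment for a noisy baseline can also introduce bias in the opposite direction, which is the reason for reporting both versions.

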6.3.4 Buccal cell collection

It is possible that single nucleotide polymorphisms (SNPs) may affect biologic response or modulate lignan concentration (e.g., CYP17). Subjects will not be stratified by specific SNPs at randomization as this would interfere with efficient study conduct, but results will be utilized in a multivariate analysis assessing change in Ki-67 and lignan levels. A DNA sample for assessment of SNPs will be obtained by rinsing with Scope® mouthwash and placing the effluent in containers provided by KUMC. Samples are stable in the mouthwash for years at room temperature with no special handling. Specimens will be shipped to the KUMC Central Collection Lab for logging and shipment to Intergenetics, Inc. for assessment by PCR-based methodology of a panel of SNPs thought to affect breast cancer risk and/or metabolic processing [114,115].

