Evaluation of agent-induced hormonal changes - We will examine whether SDG has any effects on serum levels of bioavailable estradiol, and testosterone, determined at baseline and after 12 months of study medication. We will determine whether addition of SDG alters the frequency or length of menstrual cycles. Effects on follicular reserve will be evaluated with anti-mullerian hormone in a sub-cohort of pre-menopausal women between ages 21 and 35 at study entry. Antimullerian hormone (AMH) is one of the earliest and most sensitive measures of follicular reserve declines for approximately 10 years before the cessation of menses. A distinct advantage for trial purposes is that it does not vary with day of menstrual cycle [119].

Adverse Events and Quality of Life – Change from baseline to 12 months will be assessed for mastalgia (expected in 30-50% of subjects at baseline), menstrual cycle and follicular reserve, and quality of life, as a function of SDG intake, plasma lignan levels and urinary lignan excretion. We will use the breast pain questionnaire (BPQ), which is a modified short form of the McGill Pain questionnaire (SF-MPQ) to assess breast discomfort and the Breast Cancer Prevention Trials (BCPT) Symptom Checklist to monitor quality of life

Correlative analyses will be performed with plasma and urine ENL and total lignans as the independent variable, with modifying variables of baseline BMI age and specific SNPs such as CYP17.

Since this is a phase IIB trial, the power and sample size for the primary endpoint was determined with a two-sided type I error rate of 5%. All subsequent secondary, tertiary and exploratory analyses will also be tested with a two-sided type I error rate of 5%. This may result in an elevated false positive rate for these secondary and tertiary analyses, however, since this is a Phase IIB study, we felt to control the type I error rate for the secondary, tertiary and exploratory analyses would be too conservative.

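### Best-subsets and stepwise selection in the supportive Ki-67 regression gives p-values and intervals that are not valid at their nominal level, and the plan leaves open whether post-baseline markers are candidates

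*Combined protocol and SAP*

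**What the plan says.** All of this is in section 11.2 of the combined protocol and SAP unless noted.

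- Primary analysis: "The two-sample t-test will be used to compare the change in Ki-67 between the SDG" and placebo groups. No variable selection is involved.
- Supportive regression: "Multiple regression analysis will also be used to investigate whether changes in Ki-67 are due to variables other than treatment effect". The examples given are age, cytomorphology and Gail risk, "as well as the predictive effect of other biomarkers on modulation of Ki-67".
- Method: "Best subsets and stepwise approaches will be employed while controlling for treatment group".
- The paragraph before it plans a separate correlation analysis: "We will also correlate change in the primary biomarker Ki-67 with change in other markers", with bioavailable estradiol, cytokines and RT-qPCR results as examples.
- Section 6.3.4 adds SNPs, whose "results will be utilized in a multivariate analysis assessing change in Ki-67 and lignan levels".
- Error rate: "All subsequent secondary, tertiary and exploratory analyses will also be tested with a two-sided type I error rate of 5" percent. The plan accepts in general terms that this may raise the false positive rate, and justifies it by the phase IIB setting.

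For the regression, the plan does not give the number of candidates, whether biomarkers enter as baseline values or as changes, the entry, removal or best-subset criterion, or any validation.

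**The concern.** Stepwise and best-subset methods search the data for the variables that fit best and then report a p-value for each as if it had been the only one considered. If entry requires p below 0.05, every entering predictor meets that criterion at the step where it enters, whether or not it has any relation to Ki-67. The reported p-value is then not a test of anything, and the confidence interval excludes zero by construction at that step.

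The question put to this model raises the stakes. It is meant to show whether Ki-67 change has causes other than SDG, so a spurious predictor would be read as an answer. If marker changes measured after randomisation were among the candidates, the model would also condition on variables that SDG is hypothesised to move (the secondary objectives in section 1.0 name bioavailable estradiol, adiponectin and leptin, among others). The arm coefficient would then no longer estimate the effect of SDG.

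**Working it through.** **Inputs from the plan (sections 11.1 and 11.2).** 220 evaluable women, 2:1 allocation (about 147 and 73), difference 2.5 points, SD of change 6, two-sided 5%.

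**Step 1: the plan's own figure.** SE = 6 × √(1/147 + 1/73) = 0.859. Then 2.5/0.859 = 2.91, and 2.91 − 1.96 = 0.95, so power is about 83% (82.6% by the noncentral t). The stated 83% is reproduced, and selection plays no part in it.

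**Step 2: noise candidates.** The number of candidates K is an assumption. Section 1.0 lists at least seven secondary markers, and Appendix 1, section 5.2, says a minimum of 25 genes can be measured, so 10 to 30 is a reasonable range. Forward selection with entry at p < 0.05 is also an assumption. For independent null candidates, at least one enters when the smallest of K p-values is below 0.05, with probability 1 − 0.95^K. This was checked with 2,000 simulated trials per K, with the treatment term always in the model:

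| K | 1 − 0.95^K | Simulated: at least one selected | Mean number selected | Type I error of treatment term |
|---|---|---|---|---|
| 5 | 23% | 21% | 0.23 | 4.7% |
| 10 | 40% | 41% | 0.52 | 5.5% |
| 20 | 64% | 64% | 1.04 | 5.7% |
| 30 | 79% | 79% | 1.56 | 6.5% |

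Real markers are correlated, so the exact percentages would differ. Backward elimination and best subsets were not simulated.

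The last column is a test of treatment when it has no effect. Its simulation error is about √(0.05 × 0.95/2000) = 0.5 points, so the treatment test stays near 5%, with a mild rise at K = 30.

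**Step 3: candidates that treatment cannot alter.** With a true effect of −2.5 and 20 such candidates, one of them prognostic, the mean treatment estimate is −2.50 and it is significant in 86% of runs. Baseline variables do not absorb the treatment effect.

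**Step 4: a candidate that treatment does alter.** Suppose SDG shifts a marker by s SD. The pilot table in section 2.4.4.3 makes s of about 0.5 plausible: leptin (15.7 − 12.9)/5.25 = 0.53; adiponectin (29.3 − 23.6)/11.1 = 0.51. Here ± is read as SD, the divisor is the mean of the pre and post values, and the pilot had no control arm.

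- *The marker carries a share f of the effect.* The treatment coefficient becomes −2.5 × (1 − f). With f = 0.5 that is −1.25 (simulated −1.24 to −1.32 for s = 0.5 to 1.0). With f = 1 it is 0 (simulated about 0).
- *The marker carries none of the effect but shares a cause with Ki-67 (correlation ρ).* The coefficient becomes −2.5 − 6ρs. With ρ = 0.4 and s = +0.8 it is −2.5 − 1.92 = −4.42 (simulated −4.41). With s = −0.8 it is −2.5 + 1.92 = −0.58 (simulated −0.59).

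The bias can therefore go either way. The values of f, ρ and s are assumptions; none is given in the plan for this model.

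**The case against.** The strongest reply has three parts.

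*The plan already accepts more false positives in exploratory work.* This stands in part. The 40% to 79% is numerically the familiar multiplicity figure, and the analysis is clearly not confirmatory. But the caveat concerns running many tests at 5%. It does not say that p-values from a selected model lack their nominal meaning, and it has no bearing on conditioning on variables that treatment changes.

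*Treatment is kept in every model.* This stands. A reader might infer that the regression will credit SDG's effect to other variables. The documents do not support that as stated: step 3 shows that baseline candidates leave the estimate intact, and the text never says biomarkers enter as changes. A predictive effect on modulation can be read as baseline prediction, and marker changes have their own correlation analysis. The opposite reading is also plausible, because that correlation paragraph comes directly before and the word biomarkers carries no time point. The plan should settle it.

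*Nothing decisive rests on this model.* This stands too. A reader might infer that power falls from 83% to about 31%, since in step 4 with f = 0.5 the treatment term was significant in only 31% to 35% of runs. That comparison is not sound: the 83% belongs to the primary t-test, which uses no selection, and the half share is assumed.

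**Conclusion.** The point holds for inference on the selected predictors. Following section 11.2 as written yields p-values and intervals without their nominal meaning. The chance of at least one spurious significant predictor is about 40% with 10 candidates and 79% with 30, assuming independent null candidates and forward entry at 5%.

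Distortion of the treatment coefficient is conditional. It occurs only if post-baseline markers are allowed in, and its direction depends on how the marker relates to Ki-67. The documents do not support a claim that it will occur.

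The weakness is confined to a supportive analysis and leaves the primary comparison untouched. It is a worthwhile improvement, not an obstacle to the trial.

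**What to change.** In section 11.2:

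1. Replace the selection step with one prespecified regression of Ki-67 change on arm, baseline Ki-67, the randomisation strata (site and oral contraceptive use), age, baseline cytomorphology and Gail risk. State that no post-baseline variable enters.
2. Analyse marker changes in separate arm-adjusted models, labelled exploratory or mechanistic, and say that they are not alternatives to a treatment effect.
3. If any data-driven selection is kept, list the candidates with their time points and the selection rule. Report bootstrap selection frequencies or cross-validated results, with no nominal p-values. Handle the SNP analysis of section 6.3.4 in the same way: SNPs are fixed before randomisation and cannot be altered by treatment, but selecting among a panel raises the same issue.

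The cost is SAP wording, a little more programming and fewer reported predictors. No change to sample size, data collection or the primary analysis is needed.
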